### 8.2 Adverse Events and Serious Adverse Events Evaluation and Reporting

#### 8.2.1 Adverse Events

An AE is any unfavorable and unintended sign (including an abnormal laboratory finding), symptom, or disease temporally associated with the use of a medical treatment or procedure that may or may not be considered related to the medical treatment or procedure. AE definitions will be followed as stated in the “Note for Guidance on Clinical Safety Data Management: Definitions and Standards for Expedited Reporting” (ICH topic E2A)

All AEs reported by the subjects or apparent from their physical appearance during the clinical study will be reported on the AE eCRF page.

The Investigator will assess severity for each AE and SAE reported during the study and assign it to one of the following categories, according to CTCAE 5-point scale (version 5.0). Grade refers to the severity of the AE with unique clinical descriptions of severity for each AE based on this general guideline:

- **Mild (Grade 1):** Asymptomatic or mild symptoms; clinical or diagnostic observations only; intervention not indicated.
- **Moderate (Grade 2):** Minimal, local, or noninvasive intervention indicated; limiting age-appropriate instrumental activities of daily living (ADL).
- **Severe (Grade 3):** Severe or medically significant but not immediately life threatening; hospitalization or prolongation of hospitalization indicated; disabling; limiting self-care ADL.
- **Life-threatening (Grade 4):** Life-threatening consequences; urgent intervention indicated.
- **Death (Grade 5):** Death related to AE.

If an AE has multiple aspects, the aspect with the highest severity will be graded.

It is emphasized that the term severe is a measure of severity; thus, a severe AE is not necessarily serious. An event is defined as ‘serious’ when it meets at least one of the predefined outcomes as described in the definition of an SAE, NOT when it is rated as severe. For example, itching for several days may be rated as severe, but may not be clinically serious.

In addition, clinically significant changes in physical examination findings and abnormal objective test findings (e.g., laboratory, x-ray, ECG) should also be recorded as AEs.

Any abnormal laboratory test results that meet any of the conditions below must be considered as “clinically significant”:

- Are associated with accompanying symptoms, and/or
- Require additional diagnostic testing or medical/surgical intervention, and/or

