9.1 Adverse events

Adverse events are defined in protocol Appendix 8.2.

A treatment-emergent AE (TEAE) is defined as any event not present prior to the first administration of the study drug, or any event already present that worsens in either severity or frequency following exposure to the study drug.

An AE that occurs prior to the first administration of the study drug will be considered a non-treatment emergent AE.

TEAEs will be classified and summarized as follow:

- TEAEs in pitavastatin period: TEAEs with a start date/time between first dose of pitavastatin on Day 1 and before first dose of ceftobiprole on Day 4.
- TEAEs in ceftobiprole period: TEAEs with a start date/time between first dose of ceftobiprole on Day 4 and before first dose of pitavastatin on Day 6.
- TEAEs in ceftobiprole + pitavastatin period: TEAEs with at start date/time on or after first dose of pitavastatin on Day 6.
- Overall: all TEAEs starting on or after first dose of pitavastatin on Day 1.

An overview summary of number and percentage of subjects will be provided for any TEAE, study-drug-related TEAEs, serious TEAEs, study drug-related serious TEAEs, TEAEs leading to treatment discontinuation, study drug-related TEAEs leading to treatment discontinuation, TEAEs leading to treatment interruption, study drug-related TEAEs leading to treatment interruption, TEAEs leading to death, study drug-related TEAEs leading to death. In summary tables, relationship and action taken with study drug refer to ceftobiprole or pitavastatin.

All TEAEs, non-TEAEs, serious AEs (SAEs), and AEs leading to death will be presented in separate listings.

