9.1.3 Severity of adverse event

Severity of AEs is assessed by the investigator according to CTCAE (version 5.0) as ‘Mild’ (Grade 1), ‘Moderate’ (Grade 2), ‘Severe’ (Grade 3), ‘Life-threatening’ (Grade 4), or ‘Death’ (Grade 5). A summary of TEAEs by severity will be presented in a table. If a subject reports multiple occurrences of the same AE, only the most severe will be counted. AEs that are missing severity will be presented in tables as severity ‘Unknown’.

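### SAP 9.1 counts worsening as treatment-emergent but tabulates by start time only, so a pre-dose event that worsens enters no summary column

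*SAP*

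**What the plan says.** SAP 9.1 and Protocol 3.5.1.3.1 give the same two-limb definition of a TEAE. The first limb is an event absent before the first administration; the second is "or any event already present that worsens in either severity or frequency following exposure to the study drug".

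SAP 9.1 continues: "An AE that occurs prior to the first administration of the study drug will be considered a non-treatment emergent AE". It makes no exception for an event that later worsens. The parallel sentence in Protocol 3.5.1.3.1 only calls such an event a pre-treatment AE, which describes its timing and leaves the second limb intact.

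SAP 9.1 then sets up four columns:

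- Pitavastatin: "TEAEs with a start date/time between first dose of pitavastatin on Day 1 and before first dose of ceftobiprole on Day 4".
- Ceftobiprole: "TEAEs with a start date/time between first dose of ceftobiprole on Day 4 and before first dose of pitavastatin on Day 6".
- Ceftobiprole + pitavastatin: TEAEs whose start is at or after the Day 6 pitavastatin dose.
- The total: "Overall: all TEAEs starting on or after first dose of pitavastatin on Day 1".

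AEs are collected from informed consent (Protocol 3.5.1.3.1), so events with a pre-dose start can be in the data. TEAEs and non-TEAEs are each listed (SAP 9.1). SAP Appendix 1 imputes partial start dates; it has no rule on the date of a worsening.

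**The concern.** The second limb of the definition is there for events that pre-date the first dose. The column rules then ask only when an event started, so that limb cannot bring any event into a summary table. A programmer would have to choose between the definition and the sentence that follows it.

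What is at stake is the by-period safety summary. The safety objective concerns ceftobiprole without and with a single dose of pitavastatin, and SAP 4 singles out AEs for summary by period. If a worsening is credited to an earlier column, the contrast between columns is blurred. The action-taken rows carry the same risk. Suppose an event begins on Day 2, worsens on Day 5 and leads to ceftobiprole being stopped. If it is held as one record, the discontinuation is counted in the pitavastatin column, a period in which no ceftobiprole had been given.

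**Working it through.** The plan states no figure here to reproduce. The check is to apply the four column rules to every possible pairing of start and worsening.

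Inputs, on the clock of Protocol Table 2 (hours from the Day 1 pitavastatin dose): Day 1 pitavastatin at 0 h, first ceftobiprole infusion at 70.5 h, Day 6 pitavastatin at 120 h. The intervals are therefore pre-dose (below 0), pitavastatin (0 to below 70.5), ceftobiprole (70.5 to below 120) and ceftobiprole + pitavastatin (120 and later). Assumption for the table: one record per event, keeping its original start.

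| Event starts in | Worsens in | Period column under SAP 9.1 | In Overall? |
|---|---|---|---|
| Pre-dose | Pitavastatin | none | no |
| Pre-dose | Ceftobiprole | none | no |
| Pre-dose | Ceftobiprole + pitavastatin | none | no |
| Pitavastatin | Pitavastatin | Pitavastatin | yes |
| Pitavastatin | Ceftobiprole | Pitavastatin only | yes |
| Pitavastatin | Ceftobiprole + pitavastatin | Pitavastatin only | yes |
| Ceftobiprole | Ceftobiprole | Ceftobiprole | yes |
| Ceftobiprole | Ceftobiprole + pitavastatin | Ceftobiprole only | yes |
| Ceftobiprole + pitavastatin | Ceftobiprole + pitavastatin | Ceftobiprole + pitavastatin | yes |

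All nine are TEAEs by the definition. Three (pre-dose start) enter no column, three are tabulated only in a period before the worsening, and three are placed where the worsening happened: 3 + 3 + 3 = 9. These are logical cases, not frequencies.

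Size per subject, with all 12 planned subjects in the safety set: 1/12 = 8.3 percentage points.

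- Start on Day -1, worsening on Day 5: 0/12 in all four columns as written. Counting the worsening gives 1/12 under ceftobiprole and 1/12 in Overall; the other two columns stay at 0/12.
- Headache of Grade 1 on Day 2, Grade 3 on Day 5: if it is one record graded at its worst, it is 1/12 at Grade 3 under pitavastatin and 0/12 under ceftobiprole. Counted by period, it is 1/12 at Grade 1 under pitavastatin and 1/12 at Grade 3 under ceftobiprole, with the subject counted once in Overall.

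**The case against.** The strongest reply is that the misplacement depends on a document that is not in the package. If the eCRF convention opens a new record whenever an event worsens, each record has its own start and the start-time rules place it correctly. This stands as a limit on the cross-period cases, and such a convention would also bring pre-dose events that worsen into the columns. But neither document states it, and the unqualified non-TEAE sentence would still contradict the definition.

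Nor do the documents show the opposite convention. The protocol's grading sentence, "If an AE has multiple aspects, the aspect with the highest severity will be graded", concerns the aspects of an AE when it is graded, not its course over time. The SAP 9.1.3 rule, "If a subject reports multiple occurrences of the same AE, only the most severe will be counted", is compatible with several entries for one event.

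Three stronger readings are tempting and do not hold:

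- That onset on Days 1 to 3 with later worsening is also a contradiction. It is not. Such an event is a TEAE under the first limb, and placing it in its onset period breaks no stated rule. What is missing is any count of the later worsening.
- That the rule always flatters ceftobiprole. A pre-dose event that worsens on Days 1 to 3 is lost from the pitavastatin column, so pitavastatin alone looks better. An event that starts on ceftobiprole and worsens after the Day 6 pitavastatin dose stays under ceftobiprole alone.
- That events vanish from the report. They remain in the listings. Laboratory worsening also appears in shift tables (SAP 9.3), and vital signs and ECG are summarised as changes from baseline (SAP 9.4 and 9.5).

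It is also fair that this is an exploratory study without formal hypothesis testing, and that the health criteria at entry limit pre-dose illness.

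**Conclusion.** The point holds in two parts of different strength. First, SAP 9.1 contradicts itself: a pre-dose event that worsens after first dose is a TEAE by definition, yet it is labelled non-treatment emergent and admitted to no period column and not to Overall. This follows from the text as written. Second, and only if a worsened event keeps one record and its original start, an event that crosses periods is tabulated solely in the earlier one, which blurs the comparison of ceftobiprole without and with pitavastatin.

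Each affected subject shifts a column by 8.3 percentage points, given 12 subjects in the safety set. The documents give no AE rates that would allow an expected number of such subjects, and no overall direction of bias should be claimed. The defect is confined to the AE summary tables; the primary pharmacokinetic analysis is untouched.

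**What to change.** In SAP 9.1:

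1. Restrict the non-treatment-emergent sentence to pre-dose events that do not worsen after the first dose.
2. Let Overall admit TEAEs that either start or worsen at or after the Day 1 pitavastatin dose.
3. Count an event in its onset period, if that is post-dose, at the grade reached there, and also in any later period in which it worsens, at the grade reached in that period.

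Implement the third item by instructing the site to open a new AE record, with the date and time of the change, whenever an event increases in severity or frequency. The existing start-time rules then do the assignment.

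The cost is a few words of SAP text and one eCRF instruction. The downside is that one event may appear in two period columns, so the period counts need not add up to Overall; a footnote should say so. Overall still counts the subject once, because SAP 9.1.1 already counts a subject once per category.

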9.1.1 Incidence of adverse events

If appropriate, the number and percentage of subjects reporting AEs will be tabulated by SOC and PT for all TEAEs, and separately for study-drug-related TEAEs. Subjects with multiple events will be counted only once within each category. SOC and PT will be sorted in descending order of frequency overall.

9.1.2 Relationship of adverse events to study drug

A summary of TEAEs will also be presented by relationship to study drug, SOC and PT. If a subject reports multiple occurrences of the same AE, only the worst relationship category will be counted.

Adverse events that are missing an assessment of relationship to study drug will be counted in the study-drug-related AEs summary table, but will be presented in the summary table by relationship and in listing with a 'Missing' relationship.

9.1.3 Severity of adverse event

Severity of AEs is assessed by the investigator according to CTCAE (version 5.0) as ‘Mild’ (Grade 1), ‘Moderate’ (Grade 2), ‘Severe’ (Grade 3), ‘Life-threatening’ (Grade 4), or ‘Death’ (Grade 5). A summary of TEAEs by severity will be presented in a table. If a subject reports multiple occurrences of the same AE, only the most severe will be counted. AEs that are missing severity will be presented in tables as severity ‘Unknown’.

9.2 Physical examination

Physical examination results for all subjects will be presented in a listing.

9.3 Clinical laboratory evaluations

Local laboratory tests include hematology, chemistry, urinalysis, serology, and drug and alcohol screen parameters in accordance with the protocol Schedule of Assessments and protocol Section 3.5.1.3.2.

Summary tables for hematology and chemistry parameters including actual values and change from baseline values will be presented for baseline and post-baseline scheduled assessments.

Hematology and chemistry parameters data will also be categorized as following:

- Each subject’s laboratory safety parameter values, when appropriate, will be categorized based on CTCAE version 5.0.
- Laboratory parameter values will be flagged as ‘low’, ‘normal’, or ‘high’ relative to the normal ranges of the laboratory.

These categorical data will be summarized in shift tables comparing relevant post-baseline visits with those at the baseline visit.

If any laboratory value falls above or below the upper or lower level of quantification, the following rule will be applied for summary statistics: values reported as $< XX$ or $\leq XX$ will be analyzed as $XX/2$; values reported as $> XX$ or $\geq XX$ will be analyzed as XX .

All clinical laboratory parameters will be presented in a listing including normal ranges and indicating if the value is out of range. Laboratory data collected at unscheduled visits will be included in listings only.

9.4 Vital signs

Summary tables of observed values and changes from baseline, will be presented for vital signs data, including body temperature (°C), respiration rate (breaths/minute), pulse rate (bpm), systolic blood pressure (mmHg), diastolic blood pressure (mmHg), at each visit on a given timepoint, in the Safety set.

Vital signs data collected at unscheduled visits will be included in listings only.

9.5 Electrocardiogram

Summary tables of observed values and changes from baseline, will be presented for 12-lead data, including heart rate (bpm), PR interval (msec), QRS duration (msec), QT interval (msec), QTcF interval (msec), at each visit on a given timepoint, in the Safety set.

Interpretation and ECG data collected at unscheduled visits will be included in listings only.

10 INTERIM ANALYSES

No interim analyses will be performed.

11 CHANGES IN THE PLANNED ANALYSIS

There are no changes between the protocol-defined statistical analyses and those presented in this SAP.

12 APPENDICES

Appendix 1 Adverse event and prior/concomitant medication date imputations

Imputation rules for partial dates

Adverse event start date imputation

Parameter	Missing	Additional conditions	Imputation
Start date for AEs	D	M and Y same as M and Y of first dose of study drug	Date of first dose of study drug
		M and/or Y not same as date of first dose of study drug	First day of month
	D and M	Y same as Y of first dose of study drug	Date of first dose of study drug
		Y is after Y of first dose	1 January
	D, M, Y	None – date completely missing	Date of first dose of study drug

D = day; M = month; Y = year; AE = adverse event.

Note: In all cases, if an estimated start date is after a complete stop date, use the first day of the stop date month.

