2.2 Secondary objectives

The secondary objectives are:

- To assess the pharmacodynamic (PD) effect of iv ceftobiprole on the diurnal plasma level profile of coproporphyrin I (CP-I) in healthy subjects
- To describe the systemic exposure of iv ceftobiprole without and with oral administration of pitavastatin in healthy subjects
- To assess the single-dose plasma PK of the pitavastatin metabolite, pitavastatin lactone, after a single oral dose of pitavastatin, administered without and with iv ceftobiprole in healthy subjects
- To assess the safety and tolerability of ceftobiprole without and with administration of a single oral dose of pitavastatin in healthy subjects.

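### The adverse-event date rule ignores the study periods, so events with incomplete onset dates can be counted in an earlier period, most often pitavastatin alone

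*SAP*

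**What the plan says.** SAP 4.3.3 refers to Appendix 1 for adverse-event dates, and the SAP gives no other rule. Appendix 1 has five branches:

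- Day missing, "M and Y same as M and Y of first dose of study drug": date of first dose.
- Day missing, "M and/or Y not same as date of first dose of study drug": first day of the onset month.
- Day and month missing, "Y same as Y of first dose of study drug": date of first dose.
- Day and month missing, "Y is after Y of first dose": 1 January.
- "None – date completely missing": date of first dose.

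A note adds that "if an estimated start date is after a complete stop date, use the first day of the stop date month".

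Under SAP 3.1.3 and 4.3.2, first study drug is the Day 1 dose of pitavastatin alone. SAP 9.1 defines three reporting periods by onset. The first is "TEAEs with a start date/time between first dose of pitavastatin on Day 1" and the first ceftobiprole dose on Day 4. The second runs from there to the Day 6 pitavastatin dose. The third starts with that dose and has no end point, so it also takes follow-up events. SAP 4 says adverse events are tabulated by period as well as overall. The objective these tables serve is "To assess the safety and tolerability of ceftobiprole without and with administration of a single oral dose of pitavastatin" (SAP 2.2).

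**The concern.** Imputing to first dose is a common convention. It answers one question cautiously: whether an event of uncertain date is treatment-emergent. Here the same date also decides which treatment the event is reported under. The study has a fixed sequence, so the first dose is not the drug whose safety is being assessed, and nothing in Appendix 1 refers to the Day 4 or Day 6 doses that separate the periods. An event that began on ceftobiprole, on the combination, or after discharge can therefore appear under pitavastatin alone. The by-period table is the one that addresses ceftobiprole without and with pitavastatin. With 12 subjects, a single event is visible in it.

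**Working it through.** The plan states no figure on this point, so there is none to reproduce. The check applies Appendix 1 and then the SAP 9.1 periods to each possible onset day.

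**Inputs.** By date alone, Days 1 to 3 are the pitavastatin period, Days 4 and 5 ceftobiprole, and Day 6 onward the combination (SAP 9.1). Follow-up is 5 to 9 days after discharge on Day 8 (Protocol 3.1.4): 8 + 5 = Day 13 to 8 + 9 = Day 17. Clock times on Days 4 and 6 are ignored because the SAP has no rule for a missing time.

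**Direction.** For a truly treatment-emergent event, the imputed date is Day 1, the first of a later onset month, or 1 January of a later onset year. Each is on or before the true onset. The stop-date note acts only when the imputed start is later than the stop date, which cannot happen in these cases, and it never moves a start later. So the period stays the same or becomes an earlier one.

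**Dependence on the calendar.** Day missing, 30-day month, true onset Days 4 to 17:

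| Day 1 falls on | Counted under pitavastatin | Counted under ceftobiprole | Counted under combination |
|---|---|---|---|
| 1st to 14th | Days 4–17 | none | none |
| 20th | Days 4–11 | none | Days 12–17 |
| 26th | Days 4–5 | none | Days 6–17 |
| 27th | Day 4 | Days 5–17 | none |
| 28th | none | Days 4–17 | none |
| 29th or 30th | Days 4–17 | none | none |

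With Day 1 on the 28th, the first of the next month is Day 4, so every such event lands in the ceftobiprole period. With Day 1 on the 29th or 30th it is Day 3 or Day 2, so every one lands under pitavastatin.

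**Average over Day 1 dates** (assumption: all equally likely). In a 30-day month there are 30 × 14 = 420 combinations of Day 1 date and onset day.

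- Pitavastatin: 14 × 14 = 196 (1st to 14th), plus 13 + 12 + … + 0 = 91 (15th to 28th), plus 2 × 14 = 28 (29th and 30th). Total 315; 315/420 = 75.0%.
- Onset on Days 9 to 17 only: 14 × 9 = 126, plus 8 + 7 + … + 0 = 36, plus 2 × 9 = 18. Total 180; 180/270 = 66.7%.

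Over every Day 1 date in 2025 (2024 agrees within 0.2 points):

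| True onset, day missing | Pitavastatin | Ceftobiprole | Combination |
|---|---|---|---|
| Days 4–5 | 95.1% | 4.9% | – |
| Days 6–8 | 86.8% | 6.6% | 6.6% |
| Days 9–17 | 67.1% | 6.6% | 26.3% |
| Days 4–17 | 75.3% | 6.3% | 18.3% |

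**Day and month missing.** Only a Day 1 from 16 December on can escape. Of 365 × 14 = 5,110 combinations, 1 + 2 + … + 13 + 3 × 14 = 133 have onset in the next year. For Day 1 on 30 or 31 December, 1 January is Day 3 or Day 2, so 2 × 14 = 28 of these still count under pitavastatin. That leaves 105; 105/5,110 = 2.1%, so 97.9% are counted under pitavastatin.

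**Date fully missing.** 100% go to Day 1.

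**Effect of one event.** 1/12 = 8.3 percentage points at most in any one column. SAP 9.1.1 counts a subject once per category, so the change is zero if the subject is already counted there.

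**The case against.** The strongest reply is that the rule will seldom be used. Subjects are confined from Day -2 to Day 8 with adverse-event monitoring every day (Protocol Table 1). Missing data are queried and must be explained in the report (Protocol 3.7). Follow-up comes only 5 to 9 days after discharge. The summaries are descriptive, with no hypothesis testing (SAP 4), and every treatment-emergent event is listed, so a reader can inspect individual cases among 12 subjects. Pitavastatin alone is not a named comparator in the safety objective. Any replacement rule is also a convention and will misplace some events.

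Most of this stands, and it limits the impact. It does not remove the defect: once a date is imputed, nothing downstream corrects the period. The likeliest source of incomplete dates is onset after discharge recalled at Follow-up, and all such events belong in the combination period.

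A reader might also gauge the size by elapsed time. The first infusion starts 70.5 h after the Day 1 dose, and Follow-up falls about 288 to 384 h after it. So 1 − 70.5/288 = 76% to 1 − 70.5/384 = 82% of the interval follows the start of ceftobiprole. That is a share of time under an assumed uniform onset, not a misclassification rate, and it ignores the later-month branch. The documents give no onset distribution to support it.

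**Conclusion.** The concern holds, with limits. Where the day is missing in the month of first dose, only a matching year is known, or nothing is known, later-period events are counted under pitavastatin alone. A missing day in a later month leaves the period to the calendar. The shares of about 75% (Days 4 to 17), 67% (Days 9 to 17) and 98% (year only) rest on equally likely Day 1 dates and date-only period assignment. The 100% for a fully missing date needs neither.

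Two stronger readings are tempting, and the documents do not support them. One is that every partial date is set to Day 1. The later-month and later-year branches of Appendix 1 rule that out, and about a quarter of day-missing events on Days 4 to 17 are not counted under pitavastatin. The other is that the rule can only move ceftobiprole events into the pitavastatin column. With Day 1 on the 28th of a 30-day month, it adds follow-up events to the ceftobiprole column instead. What is one-way is movement to an earlier period, and only for events that are truly treatment-emergent. A pre-treatment event with a missing day in the same month as first dose would move forward to Day 1.

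Overall totals of truly treatment-emergent events are unchanged. The practical effect is probably small, but the error is systematic and cheap to remove.

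**What to change.** Make Appendix 1 period-aware, before database lock:

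1. Use all recorded information (known month and year, stop date, onset before or after discharge) to limit the possible onset dates.
2. If those dates fall in one period, assign that period. Onset known to be after discharge goes to the ceftobiprole + pitavastatin period.
3. If more than one period remains possible, use the date of the first ceftobiprole dose (Day 4) if it fits the recorded parts. Otherwise use the earliest compatible date on or after Day 4. For example, with Day 1 on the 27th of a 30-day month and an event recorded in the next month, Day 4 is the 30th and does not fit, so Day 5 is used. A recorded month is never overridden.
4. Use Day 1 only when the recorded information places onset before Day 4.
5. If the date is known to be Day 4 or Day 6 but the time is missing, keep the date and assign the period that starts with that day's dose.
6. Flag imputed events in the listing.

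The cost is some appendix wording and a few lines of derivation code. The downside is that a few true pitavastatin-alone events, or pre-treatment events, may be counted under ceftobiprole. That is the conservative direction for the drug under study.
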